#### **2.6.4 Data and Safety Monitoring**

Study data monitoring will be carried out throughout the study as part of the monitoring and evaluation activities.

The practical monitoring and evaluation activities and the structuring and processing of data will be carried out by a group formed within the framework of the management of the research project - representatives of the research centers, the sponsor and the research team.

The study sponsor will discuss the results of the study data monitoring. Because the study contains minimal risks and dangers for the study participants, but provides for double-blind randomization for the selection of the study-specific treatment interventions, includes concerns on a highly-specialized clinical practice area, considers a 12-month observation period for the study participants and may have an impact on current clinical practice monitoring process will also be cooperated by the Institutional Review Boards (IRBs) of the study centers involved.

The study monitoring and evaluation team observes study activities at study centers and assesses the safety, scientific and practical relevance, consistency and continuity of data collected. IRBs monitor and evaluate the confidentiality of data collection and management, ethical issues of clinical case management and safety at clinical centers.

The study monitoring and evaluation team consists of specialists with experience in conducting research and evaluations, data management, issuing recommendations and advice on the scientific aspects of research, who are not directly involved in the implementation of this research, do not have intellectual and financial conflicts of interest and formed preconceived ideas and biases concerning the research problem.

The functions of the study monitoring and evaluation team are to observe and evaluate the following processes:

- Involvement of research participants;
- Compliance of research procedures with the research protocol;
- Safety of collected data and their scientific processing;
- Research progress;
- Compliance of the collected data on important adverse clinical events with the clinical endpoints;
- Follow-up management needs of the trial participants;

The IRBs' roles and responsibilities concerning the trial monitoring and evaluation team are defined by oversight of the ethical issues and the safety of the trial participants. In addition, they also discuss the safety of data management procedures and relevant data protection issues.

The monitoring and evaluation team operating within the study management will regularly submit reports for the sponsor's review.

Safety monitoring will be carried out as part of the monitoring and evaluation activities throughout the study. Study monitoring and evaluation procedures address the assessment and avoidance of threats to the safety of study participants, restrictions on freedom of choice, and breaches of confidentiality. Chapter 2.5.8 - Safety Assessment and Control presents the framework for these activities.

### **3.0 Risk Analysis**

#### **3.1 Expected Risks**

No specific health risks are associated with study activities or procedures for study participants. CYP2C19 \*2, \*3 genotyping with the RT-PCR-based allele discrimination method, applied on randomly selected patients in the experimental arm, belongs to the category of diagnostic procedures that do not involve health risks.

Investigational medicinal products used in the study also do not pose additional health risks to patients. Antiplatelet drugs selected for treatment interventions are real-world clinical practice drugs for the study participants' treatment in conditions with clinical characteristics of study interest. Current guidelines recommend routine use of these medications in post-PCI settings. The use of the investigational product, based on the results of CYP2C19 \*2, \*3 genotyping, is a patient-centered and precision treatment selection approach that increases the chances for prevention of MACCE. Thus, it represents a significant benefit to patients and cannot be considered a health risk determinant.

Non-adherence is a significant problem in the use of long-term antiplatelet treatment with P2Y12 inhibitors. As part of the clinical follow-up provided by the study investigators and healthcare team, patients included in the study will be assessed for adherence to treatment using the BMQ. The questionnaire will assess adherence not only to P2Y12 inhibitors but also to other medications used to reduce the risk of CAD in the patients included in the study. Accordingly, this study procedure will make it possible to identify and prevent non-adherence to drug treatment (sporadic or recurrent), which will significantly reduce the possibility of developing MACCE and thus be beneficial for the subjects included in the study.

The health risks for study participants are related to the development of the disease/condition under study, CAD, MACCE (cardiovascular death, nonfatal myocardial infarction, recurrent angina, repeat PCI, stent thrombosis, ischemic stroke, transient ischemic attack, intracerebral hemorrhagic stroke), and known, expected, adverse effects of drug treatment (intracerebral hemorrhage, GI bleeding, other bleeding, thrombotic thrombocytopenic purpura). However, these cannot be considered as health risks related to the study. Such adverse events may develop in real-world practice even outside of research interventions.

Health risks may arise from inappropriate or erroneous medical care outside the study's scope and centers. The study procedures include follow-up of results from health care provided outside of study centers and scope for preventing related adverse effects.

Risk management procedures are outlined in the study protocol in Chapter 2.5.8, Safety Assessment and Control.

Additionally, diagnostic tests for the initial assessment and follow-up of study participants allow for identifying, assessing, and preventing risks from other comorbidities. Significant comorbidities that are difficult to control with the study measures or that may contribute to adverse drug reactions are excluded from the study, see Chapter 2.4.4 Exclusion Criteria.

The main study objectives include following up MACCE after ePCI in CAD cases over 12 months using widely used clinical diagnostic methods in real-world practice. These measures significantly increase the ability to identify and prevent MACCE risks and, therefore, will benefit the study participants.

The study may involve risks of limiting study participants' independence of choice and breaching confidentiality. To avoid it, special study data management operations will be implemented:

- Achieving the study participants' informed consent to participate in the study, based on complete written and verbal information about the study operations and making an independent decision;
- Data collection and processing procedures by the 2018 EU General Data Protection Regulation (GDPR);
- Monitoring and evaluation
  - Measures that will identify possible deviations from the study protocol and make it possible to prevent them.
  - Results and risks related to individual clinical cases that will be reviewed;

With consistent implementation of the study procedures, the expected benefits of the study will significantly outweigh the risks.

### 3.2 Adverse Event Reporting

#### 3.2.1 Definition of an Adverse Event

**Major Adverse Cardiovascular and Cerebrovascular Events (MACCEs):** A clinically significant adverse cardiovascular and cerebrovascular clinical event that occurs in CAD cases, which may be recurrent, incidental, with a frequency consistent with that expected in the course of the disease and the natural history of the disease (Hazard Ratio [HR], 1.26–5.68, 95%CI [4,5,7,18,23]), is quite common (1–10%) in terms of its probability, is severe in terms of its outcome, is associated with the impact of the risks associated with the disease even under optimal management, is clinically serious, may lead to death, may change the course of the disease/clinical condition, and is not preventable. MACCE determines the outcome of the clinical cases in the study and is, therefore, considered a study clinical endpoint. These include: Cardiovascular death, Nonfatal myocardial infarction, Recurrent angina, Stent thrombosis, Repeated PCI, CABG, Ischemic stroke, Transient ischemic attack, Intracerebral hemorrhage, Atrial fibrillation, Heart failure.

**Anticipated Adverse Medication Effect (AAME):** A serious adverse effect on the patient's health or a life-threatening problem or death associated with a medicinal product, in cases where the cause of the clinical effect, problem or death is already established and is consistent with previously studied possible effects of the medicinal product in its nature, severity or frequency of occurrence; an expected serious problem with the medicinal product that is related to the safety of the study participant. Possible adverse effects associated with treatment with clopidogrel, prasugrel, or ticagrelor are expected and are considered clinical outcomes and are considered clinical endpoints of the study: Bleeding requiring hospitalization, Thrombotic thrombocytopenic purpura, Minor or minimal bleeding, Change/discontinuation of P2Y12 inhibitor.

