## **2.5.6 Withdrawal from the Study due to Non-adherence to Treatment**

Non-adherence to the study of treatment with clopidogrel, alternative antiplatelet or other prescribed medication or a patient's decision to avoid or discontinue study procedures is grounds for withdrawal from the study due to non-adherence.

Evaluations for medication non-adherence should be performed at each study-planned follow-up visit using the Brief Medication Use Questionnaire (BMQ) [26].

No single (so-called "gold standard") tool is presented for assessing non-adherence to medication treatment. The highly specific and sensitive BMQ, currently being developed, was selected for the assessment of non-adherence to treatment. Based on characteristics of drug consumption by evaluating (scaling) the responses to nine simple questions and amounts of medication taken "during the past week" and the patient's opinion on the effects, adherence to medication treatment can be calculated. Assessments carried out during the observation period will reveal possible barriers that lead to non-adherence. The results of the assessment of the medication regimen, trust in treatment, and attitude determine the state of repeated or sporadic non-adherence or adherence. To influence the identified factors of non-adherence, the patient will be consulted during the observation period, and it will be possible to overcome sporadic non-adherence cases.

In the event of repeated non-adherence, procedures for withdrawing the patient from the study will be considered.

These procedures include:

- Informing the patient about his/her withdrawal from the study;
- Justification of the decision to withdraw the patient from the study;
- Conducting follow-up assessments of clinical outcomes;
- Clinical examinations are conducted to assess the patient's current condition and safety;

In cases where a patient is withdrawn from the study due to non-adherence to medication treatment during the 3rd, and 6th month of follow-up, a new study subject may be included in the study in his/her place, with allocation to the appropriate experimental or control group. After the 6-month follow-up period, a patient withdrawn from the study should not be replaced by a new study subject.

Withdrawal from the study will be reviewed by the study center investigator, principal investigator, and data management team. The patient will be informed of the non-adherence case and the decision to withdraw from the study.

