## **2.6 Evaluation of Study Results**

### **2.6.1 Study Endpoints**

The study follow-up results will be discussed and presented by study arms, as well as concerning the primary and secondary endpoints of the study.

The study results will also be discussed concerning other endpoints, which will be represented by clinical or non-clinical data and characterize the factors that affect the efficacy of antiplatelet treatment and determine the clinical and non-clinical outcome in the course of the CCSs both with and without the results of CYP2C19 genotyping.

The indicators for assessing the effectiveness of the study are presented in Appendix 5.

In the study, the selection of treatment regimens with clopidogrel and an alternative P2Y12 inhibitor will be carried out by determining the genotype of the CYP2C19 \*2, \*3 non-functional alleles. Clopidogrel will be used in study participants with CYP2C19 \*2, \*3 normal allele genotypes and in the control arm of study participants not undergone CYP2C19 genotyping – unspecified CYP2C19 genotype. Study participants with CYP2C19 \*2, \*3 non-functional allele genotypes will be given alternative antiplatelet therapy.

In cases of CAD, regardless of treatment with P2Y12 inhibitors after ePCI, the clinical endpoints will be represented with MACCEs and other clinical conditions related to CAD or the potential adverse events of antiplatelet drug treatment. The incidence of the primary, secondary and other study endpoints defined as clinical outcomes of CYP2C19 genotype-guided P2Y12 inhibitor treatment will be assessed in the study arms.

The primary endpoints of the study are defined as:

- Number of study participants who died from any cause (Death from Any Cause) within a 12-month of the study follow-up;
- Number of study participants who died from any cardiovascular cause (Death from Cardiovascular Cause) within a 12-month of the study follow-up;

The secondary endpoints of the study are defined as:

- Number of study participants who experienced non-fatal myocardial infarction (Non-fatal Myocardial Infarction) within a 12-month of the study follow-up;
- Number of study participants who experienced unstable angina or angina requiring hospitalization (Unstable Angina) within a 12-month of the study follow-up;
- Number of study participants who experienced a stroke or transitory cerebral ischemic event (Stroke or TIA) within a 12-month of the study follow-up;

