### **3.2.6 Adverse Event Reporting**

Any MACCE or AAME observed or voluntary adverse event occurring in a trial is identified by the investigator or sponsor. Information about it is submitted to the trial participant's medical care team, who should then direct the clinical case management.

A MACCE or AAME event is recorded:

- In the study data registration form;
- A description and significance of the event are recorded in the routine medical documentation;

After the registration of the MACCE or AAME event, the participant will be withdrawn from the study.

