## **3.3 Early Withdrawal of a Study Participant**

A study participant may withdraw from the study at any time during the study and for any reason, whether identifiable or not, by their own free will. This decision and the patient's independent choice are presented in the informed consent form.

A study participant may also be withdrawn early from the study if there is persistent non-adherence to the study follow-up and treatment procedures (see Chapter 2.5.6, Withdrawal from the Study Due to Non-Adherence to Treatment).

A study participant may be withdrawn early from the study based on a clearly stated justification by the investigator or the study sponsor if it is in the patient's best interests to discontinue the study.

The basic reasons for withdrawal from the study are considered as follows:

- If any abnormal study result, symptom, or measurement parameter is detected and resolution, improvement, correction or stabilization of which may require a long period of treatment and/or observation and will change the course of the study-defined follow-up and treatment;
- Any adverse event that may persist during the follow-up period, or require a change or discontinuation of the study-defined treatment, or disrupt the study-defined clinical evaluation plan, or be associated with a severe outcome.
- Any adverse event that may be masked by the use of different medical care regimens than those specified in the study protocol;
- If study treatment intervention, it may pose an expected AAME, a health threat, requiring discontinuation and modification. These conditions require modified treatment measures and regimens other than those specified in the study, including hospitalization. In addition, clinical conditions that may be characteristic of AAME may be exclusion criteria from the study.
- An adverse event related to treatment with P2Y12 inhibitors is a study endpoint, after which the study-planned follow-up is no longer required.
- The MACCE determines the study endpoint, and further measures are no longer required.

In these cases, study participants are discontinued from the study-planned follow-up; the necessary assessments of early withdrawal from the study should be conducted, and the reason for early withdrawal from the study should be determined (evaluated). In these cases, the patient continues to be monitored and treated by the medical support team.

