The investigator will describe and analyze the reason for the study participant's early withdrawal, which is part of the routine medical records. An adverse clinical event will be registered in the study data form.

The investigator will inform the study participant of the decision to withdraw from the study early and about further follow-up and treatment measures.

Patient data collected before withdrawal will be used for study purposes, with confidentiality, following the procedures provided and the terms presented to the patient in the informed consent form.

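### A later P2Y12 drug change or stop, or the adverse effect behind it, can end observation of the 12-month endpoints, and the text is ambiguous about when

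*Combined protocol and SAP*

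**What the plan says.** Section 3.2.1 defines an AAME as a serious effect of a medicine whose cause is already established. It then names the possible adverse effects of the three P2Y12 inhibitors that are to count as clinical endpoints: bleeding that leads to admission, TTP and, closing the list, "Minor or minimal bleeding, Change/discontinuation of P2Y12 inhibitor". Drug change or discontinuation does not appear among the endpoints in the Synopsis or Section 2.6.1, and has no row in Appendix 3.

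The consequence of an AAME is set in Section 3.2.6: "After the registration of the MACCE or AAME event, the participant will be withdrawn from the study". Section 3.3 adds "An adverse event related to treatment with P2Y12 inhibitors is a study endpoint, after which the study-planned follow-up is no longer required", and gives as a further withdrawal reason an adverse event that may "require a change or discontinuation of the study-defined treatment". For all the reasons it lists, "In these cases, study participants are discontinued from the study-planned follow-up". On data, it says only that "Patient data collected before withdrawal will be used for study purposes". Section 2.5.6 has a parallel route: "In the event of repeated non-adherence, procedures for withdrawing the patient from the study will be considered".

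The first primary endpoint is "Number of study participants who died from any cause (Death from Any Cause) within a 12-month of the study follow-up". Cardiovascular death and the secondary clinical endpoints have the same 12-month horizon.

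**The concern.** The trial compares strategies for choosing a P2Y12 inhibitor and asks how they perform in real-world practice. Switches and stops after assignment are part of how a strategy performs, so outcomes after them belong in the comparison. If a change or stop, or the adverse effect that led to it, takes the participant out of follow-up, later deaths, infarctions and strokes are not collected.

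Such loss need not be random. Section 2.5.4 discloses the allocation and genotyping results to participants and the medical care team. Arm 2 takes ticagrelor or prasugrel, while arms 1 and 3 take clopidogrel. Rates of change, and the reasons for it, can therefore differ by arm and be related to risk.

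The planned summaries do not repair this. The Appendix 3 rates divide by all participants of an arm, and its hazard ratio is a ratio of proportions. With no rule for withdrawn participants, someone who leaves early would in effect be counted as event-free. In the Cox model of Section 2.6.3 the same person would be censored, which is informative if those who stop are at different risk. Withdrawal for any reason is itself a reported endpoint, so the loss would be visible, but the missing outcomes would not be recovered.

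**Working it through.** **The text, step by step**

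1. Trigger. The lead-in in Section 3.2.1 (possible adverse effects of treatment) and the word serious in the AAME definition point to changes caused by a drug effect. The item itself states no reason, duration or severity, and the same list includes minor bleeding, which is not serious. Both readings are open.
2. Consequence. Section 3.2.6 withdraws after a registered AAME and states no exception. Section 3.3 reaches adverse-event-driven changes independently of the list item.
3. After withdrawal. The Synopsis plans one evaluation within 72 hours. Appendix 2 has a withdrawal column and nothing beyond it. Section 3.4 accepts that the participant's study period is then shorter. Later monitoring under Section 3.3 is clinical care. No section provides endpoint or vital-status collection to month 12.

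**Size**

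The plan has no figure on this point to reproduce: no rate of drug change or stop is given. Section 2.4.2 expects 25% non-completion for all reasons (240 × 0.25 = 60), which cannot be split by cause.

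Inputs from the documents: N = 240; arms of 110, about 50 and 80 (Section 2.4.2); MACCE probability 1–10% (Section 3.2.1). Assumptions: that range read as a 12-month risk *r*; a share *s* who change or stop; uniform timing, so half the year is lost on average; observation ends at the change.

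Share of observation lost = *s* × 0.5. Events lost = 240 × *s* × *r* × 0.5.

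| *s* | participants | observation lost | lost at *r* = 1% | lost at *r* = 10% |
|---|---|---|---|---|
| 2% | 4.8 | 1% | 0.024 of 2.4 | 0.24 of 24 |
| 5% | 12 | 2.5% | 0.06 of 2.4 | 0.6 of 24 |
| 10% | 24 | 5% | 0.12 of 2.4 | 1.2 of 24 |

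Death, at an assumed 12-month mortality of 1–2% and *s* = 10%: 24 × 0.01 × 0.5 = 0.12 of 2.4, up to 24 × 0.02 × 0.5 = 0.24 of 4.8.

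If risk is multiplied by *k* after stopping (assumption; *s* = 10%, *r* = 10%), lost = 24 × 0.05 × *k* and total = 216 × 0.10 + 24 × (0.05 + 0.05*k*):

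- *k* = 2: 2.4 of 25.2 = 9.5%
- *k* = 3: 3.6 of 26.4 = 13.6%

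Arm difference, with equal true risk, whole-arm denominators and withdrawn participants counted as event-free. The share of events seen is 1 − *s*/2. Assume *s* = 10% in arm 2 and 5% in arms 1 and 3:

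- Arm 2 vs arm 3: 0.95 / 0.975 = 0.97
- Arms 1+2: *s* = (110 × 0.05 + 50 × 0.10) / 160 = 6.56%; vs arm 3: (1 − 0.0328) / 0.975 = 0.99

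A wider, equally unsourced imbalance, under constant hazards with true risk 5%: the observed risk is 0.0488 at *s* = 5%, 0.0449 at 20% and 0.0421 at 30%. The apparent ratios are 0.92 and 0.86. The arm with more stopping looks better than it is.

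**The case against.** The narrower reading of Section 3.2.1 is natural. The item sits under a heading of adverse drug effects, Section 3.2.5 puts investigator or sponsor review before classification, and the separate bullet in Section 3.3 on adverse events that force a treatment change would be largely redundant if every change were already an AAME. This stands to the extent that the text is ambiguous. It does not settle the matter, because minor bleeding is listed too, and Section 3.2.5 keeps the classification even when the relationship is doubtful.

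On that narrower reading the list item adds little. A change due to bleeding is already caught through the bleeding, one due to another adverse event through Section 3.3, and non-adherence through Section 2.5.6. This also stands, and it is why the point concerns the withdrawal rule as well as the list.

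Some text softens the rule. Section 3.2.7 lets the IRB recommend further follow-up; this conflicts with Section 3.2.6 but does not cancel it. Section 3.2.3 follows an adverse effect until it resolves or stabilises, which is not follow-up for death or infarction. Section 2.4.2 treats assessments made before or at withdrawal as data, and Section 2.5.6 includes outcome assessments and only considers withdrawal. None of these secures observation to month 12, but together they mean that a change can end follow-up, not that it always does.

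Finally, the base-case figures are small, and the larger ones need high stopping combined with raised risk or a wide arm imbalance, none of which the documents supply. Counting withdrawn participants as event-free is an inference from the Appendix 3 denominators, not a stated rule.

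**Conclusion.** The point holds in this form: a later drug change or stop, or the adverse effect behind it, can end observation of the 12-month endpoints, and Section 3.2.1 leaves unclear which changes qualify. At 2–10% stopping unrelated to risk, 1–5% of event observation is lost. With doubled or tripled risk after stopping, at the top of the assumed ranges, the loss is about 10–14% of MACCE. A 10% versus 5% imbalance moves the apparent risk ratio from 1 to 0.97 or 0.99. All of this rests on assumed stopping rates and timing. The effect is modest unless stopping is tied to risk or differs widely by arm.

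A reader might infer that every drug change removes a participant automatically. The documents do not support that, given the lead-in in Section 3.2.1, the classification step and the IRB step. Nor do they show that the genotype-directed choice at allocation is a trigger, since it is the assigned treatment. Whether a pause before surgery (narrative of Section 2.4.4) counts is unclear, and nothing here depends on it. A reader might also infer that the trial's result must be materially biased; without a rate of change, that cannot be shown.

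**What to change.** - Section 3.2.1: remove drug change or discontinuation from the AAME and endpoint list. Record each later change, pause, restart or stop as dated treatment status with drug and reason.
- Section 3.2.6: replace the withdrawal sentence as it applies to AAMEs. State that an AAME may end study treatment but not endpoint follow-up, which continues at the scheduled visits, or by vital-status and record check, to month 12 unless consent is withdrawn.
- Sections 3.2.7, 3.3 and 2.5.6: say the same for a treatment change, pause, stop or non-adherence.

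Relabelling alone is not enough. Reporting the causal effect as the AAME would still lead to withdrawal under the present Section 3.2.6, and merely aligning that section with 3.2.7 would leave follow-up to the IRB's recommendation. Whether follow-up should also continue after a MACCE is a wider question about the same rule and is not settled here.

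The cost is wording in five sections and a few dated fields in the data record form. Visits already in the schedule would continue for participants who would otherwise have left. No planned analysis is lost, because the item is in no endpoint list in the Synopsis or Section 2.6.1 and in no Appendix 3 row.
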